2.2.5 Cross Reactivity Between Penicillin and Cephalosporins

There is an extensive literature on the chemistry of B-lactams and the cross reactivity of penicillin and cephalosporin allergy. From a chemical basis, the key issue is the “R” group modifying the B-lactam ring. The literature is consistent in concluding that cross reactivity in clinical practice is highly overestimated. The most extensive recent review (2018) by Zagursky³⁰ reviewed cross reactivity in PCN allergy, including an extensive review of the chemical structures and a review of studies, which showed that there was limited cross reactivity between PCN and cephalosporins, even early generation cephalosporins compared to later generation cephalosporins. They concluded that *“there is ample evidence to allow the safe use of all but a few early generation cephalosporins in patients with penicillin or amoxicillin allergy. Patients with a history of penicillin allergy do have a general elevated risk of allergic reaction and may develop an allergic response to cephalosporins by coincidence, but the risk is comparable to that of receiving a sulfonamide antibiotics”*.

2.2.6 Moving Forward: Extending PCN (B-lactam) Allergy Testing and a Path to Improve STD Care

Increased interest in PCN (B-lactam) allergy testing and defining patient status has been driven by parallel trends which have included:

- Recognition that most patients who report PCN (B-lactam) allergy are actually not allergic;
- The public health crisis of antimicrobial resistance and recognition that alternative therapies for B-lactam drugs are often more broad-spectrum and may facilitate development of resistance;

- Recognition that overall clinical care costs may be higher in patients who are treated with alternative regimens;
- Recognition that alternative regimens are not as effective as B-lactam primary regimens.

As a result, there has been an explosion of interest in extending PCN (B-lactam) testing outside the traditional allergy office. In December 2018 and January 2019 alone, major reviews of this topic were published in the *Lancet*¹ and *Journal of the American Medical Association*,² both publications accompanied by educational materials to facilitate increased diagnostic testing.

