4 STUDY DESIGN

This will be a multicenter study screening approximately 5,000 men and women (to achieve 1,000 evaluable participants) from different geographic areas of the US over a 14-16-month recruitment period (200 participants per site over the recruitment period). We will screen and enroll eligible individuals coming for care at ambulatory STD clinics and similar venues who self-report a history of PCN allergy.

Two methods of validating PCN allergy will be used:

- **Method 1 – PCN Skin Test (PST) Group:** skin testing of subjects with low-risk history followed by one-step oral challenge of subjects with negative skin tests.
- **Method 2 – Direct Oral Challenge (DOC) Group:** direct two-step oral challenge of subjects with low-risk history.

Each site will perform both methods, using a sequential enrollment process (See Section 4.1). All participants will be administered the same PCN (B-lactam) allergy history screening questionnaire.

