5.2 Inclusion/Exclusion Criteria

5.2.1 Subject Inclusion Criteria

Subjects must meet all the following inclusion criteria to be eligible to participate in the study:

- 18 years of age or older
- Be able to provide informed consent
- Report having a history of allergy to PCN or B-lactam drugs

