6.1.1 Screening

Screening will occur through mechanisms allowable at the individual sites including virtual screening and/or referral of individuals who have a prior history of reporting PCN allergy. If waiting room recruitment is permitted, study staff will approach potential subjects systematically, inform them that we are doing a study to optimize antibiotic use in ambulatory STD settings and ask if they were ever told they had an allergy to PCN or similar antibiotic. Subjects who report an allergy will be asked if they are interested in participating in the study. If the subject expresses interest, study staff will review the inclusion/exclusion criteria checklist to ensure the subject is eligible for enrollment. We will use standardized and Institutional Review Board (IRB)-approved screening scripts at all sites. All participants who are eligible for enrollment will be assigned a unique 5-digit participant number (PN). The same PN will be used if the participant is enrolled.

In some clinics, direct recruitment in the waiting room is not permitted. In these cases, we will post study advertising materials in the clinic waiting area promoting a study for individuals who have a history of PCN or B-lactam allergy. The clinic receptionist can also provide information to patients at time of registration. The recruitment materials will ask, “Do you have a history of penicillin or other antibiotic allergy?” or, “Have you ever been told that you are allergic to penicillin or other antibiotics?” Patients will be instructed to contact study staff in the clinic. Clinic providers may also refer patients to the study team.

Some clinics collect drug allergy information in the pre-visit medical history form. In these settings we will use a Health Insurance Portability and Accountability Act (HIPAA) Waiver of

Authorization to pre-screen potential subjects' medical records for drug allergy. Interviewers will confirm that the drug allergy is to PCN or B-lactam.

If a potential participant meets all inclusion/exclusion criteria but declines to consent or enroll in the study, study staff will record the reason they are not interested in participating in the study on a case report form (CRF). No identifying participant information will be collected unless the participant consents for enrollment.

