6.3.3 Final Outcomes and Determination of Allergy Status

If vital signs (including peak flow) and focused PE are within reasonable limits after the applicable observation periods, subjects will be counseled that they do not have an allergy to PCN (B-lactams). They will be provided with written documentation that they will be encouraged to share with their medical providers, including the STD clinic and their primary care physician (if they have one).

Final outcomes of the oral challenge will be recorded on a CRF as no reaction (negative), reaction (positive) or unevaluable (if the participant leaves the clinic before the applicable observation period is completed). If there is a reaction, after providing standard treatment, study staff will record the type of reaction, severity and how long after the amoxicillin was administered it occurred on the oral challenge testing results CRF.

If reactions to the amoxicillin oral challenge occur, they will be graded and documented using the Toxicity Table (Appendix C).

Rarely, an oral challenge in an individual who skin tests negative can produce an acute reaction (e.g., anaphylaxis) requiring emergency care. Unexpected reactions that place a subject at increased risk will be treated as necessary and reported to the IRB and DMID as required.

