APPENDIX B: PCN (B-LACTAM) ALLERGY HISTORY SCREENING QUESTIONNAIRE

Section 1: Allergy History

- 1) How long ago was the reaction to the antibiotic?
 - a. < 6 months
 - b. 6 months-1 year
 - c. 2-5 years
 - d. 6-10 years
 - e. > 10 years
 - f. Don't remember / Unknown

- 2) What was the name of the drug you reacted to?
 - a. (Please list) _____
 - b. Don't remember / Unknown

- 3) How was the antibiotic administered?
 - a. Pill or Liquid by mouth
 - b. Injection (a shot) into a muscle or through a vein
 - c. Don't remember / Unknown

- 4) When did your allergic reaction to the antibiotic start?
 - a. Less than 1 hour after the first dose
 - b. Between 1 and 6 hours after the first dose
 - c. More than 6 hours, but less than 24 hours after the first dose
 - d. 24 hours or more after the first dose
 - e. Unknown

- 5) How many days did you receive your antibiotic treatment?
 - a. One day only
 - b. About _____ days of treatment
 - c. Don't remember / Unknown

- 6) People experience many different kinds of symptoms during an allergic reaction to an antibiotic. What were the symptoms of your allergic reaction? (OK to select more than one)
 - a. Can't remember (check only after reading entire list)

- b. Non-specific symptom(s) (e.g., "sick" "thought I was a goner" "high as a kite" "like I had the flu")

Responses to the symptoms listed below should be graded on a 5-point scale:

Don't Recall /None / Mild / Moderate / Severe

Low-Risk Allergy History

- a. Isolated GI upset (*diarrhea, nausea, vomiting, abdominal pain*)
- b. Chills (*rigors*)
- c. Headache
- d. Fatigue
- e. Itching (*pruritus*), self-limited,
- f. Rash (*including maculopapular rash*)
- g. Hives (greater than 5 years ago)
- h. Flushing / redness
- i. Family history
- j. Patient denies allergy history but is in medical record

Higher-Risk Allergy History: Skin Testing and Oral Challenge Contraindicated

- a. Angioedema or swelling of lip, tongue, or around eyes
- b. Wheezing / chest tightness moderate or severe shortness of breath
- c. Throat tightness which affected ability to breathe
- d. Hypotension without rapid recovery
- e. Arrhythmia / irregular heartbeat or palpitations
- f. Syncope / pass out / dizzy
- g. Anaphylaxis or sudden drop in blood pressure
- h. Hives (5 years or less)

Late Effect Symptoms (higher-risk events occurred >24 hours after drug administration)

- a. Stevens-Johnson syndrome (*Loss >10% of skin*)
- b. Organ injury (*liver, kidney*)
- c. Low Platelets

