1. INTRODUCTION

This is a multicenter clinical study to screen and enroll eligible individuals coming for care at ambulatory STD clinics and similar venues who self-report a history of PCN or other beta-lactam antibiotic allergy. The study will screen approximately 5,000 men and women to achieve 1,000 evaluable participants from 5 study sites in different geographic areas of the US over a 14-16-month recruitment period.

Two methods of validating PCN allergy will be used:

- **Method 1 – PCN Skin Test (PST) Group:** skin testing of subjects with low-risk history followed by one-step oral challenge of subjects with negative skin tests.
- **Method 2 – Direct Oral Challenge (DOC) Group:** direct two-step oral challenge of subjects with low-risk history.

Each site will perform both allergy validation interventions, Method 1 PST Group and Method 2 DOC Group. The anticipated enrollment at each site will be approximately 200 subjects overall with 100 in each group. Since each intervention has different logistical considerations, sites will enroll subjects in sequential block groups of 25. Sites will be assigned the order of block groups randomly. Each site will plan to enroll 8 block groups, 4 in each allergy validation intervention.

The analysis plan provides additional details regarding the planned statistical analysis of the study protocol (version 2.0, 09March2020). Tables, figures and listings shells will be developed prior to the start of data cleaning and included as an appendix to a future version of the plan.

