7.3 Analysis of Primary Objective

The primary analysis will be performed on the Treated population and Per Protocol population. Estimates with corresponding exact (Clopper-Pearson) 95% confidence intervals for the following measures will be provided:

- The prevalence of PCN reactivity validated either by skin test or by direct oral challenge among those participants who report a history of PCN (B lactam) allergy and who have low-risk histories.
- The NPV on true PCN (B-lactam) allergy of the algorithm / PCN (B-lactam) allergy history screening questionnaire performance in the Treated population.

The NPV for each low-risk allergy item listed on the questionnaire will be estimated and will be compared with the prevalence of PCN reactivity using exact test of binomial proportion. The p-values will be adjusted with Benjamini-Hochberg procedure.

To construct a short standardized post-study questionnaire (4-6 questions) from the PCN (B-lactam) allergy history screening questionnaire, we will first use the item-characteristic curve from Item Response Theory (IRT) to evaluate each question item's discrimination ability of true PCN (B-lactam) allergy and use variable importance evaluation functions to indicate which questions are most useful for predicting the true PCN (B-lactam) allergy. Based on the results of IRT and variable importance analyses, we will then apply machine learning approaches such as random forest (Svetnik et al., 2003) via R package caret, to select a short post-study questionnaire that has the highest NPV among those possible short questionnaires with 4-6 selected questions.

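### The primary target is worded as PCN (B-lactam) allergy, but every reference test is a penicillin and people reporting only a cephalosporin allergy are eligible and pooled

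*Protocol*

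**What the plan says.** **Who is admitted.** Protocol 5.2.1 requires subjects to "Report having a history of allergy to PCN or B-lactam drugs"; protocol 5.1 and SAP 4.2 agree. The SAP introduction describes people who "self-report a history of PCN or other beta-lactam antibiotic allergy". Where records are pre-screened, protocol 6.1.1 states: "Interviewers will confirm that the drug allergy is to PCN or B-lactam". Protocol section 4 is narrower, describing people "who self-report a history of PCN allergy", and section 8.2 counts its 988 subjects as people with a PCN allergy history.

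**What is tested.** Skin testing uses PRE-PEN and penicillin G (protocol 6.2). Both oral challenges use amoxicillin (6.3.1, 6.3.2). No cephalosporin is used.

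**What the protocol says about carry-over.** Section 2.2.5 names the R group as the key issue and reports "limited cross reactivity between PCN and cephalosporins". Section 2.1 says the same of third-generation cephalosporins.

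**What is concluded.** SAP 7.3 estimates "The NPV on true PCN (B-lactam) allergy of the algorithm" in everyone who received either method. After a negative challenge, protocol 6.3.3 says "subjects will be counseled that they do not have an allergy to PCN (B-lactams"); 6.3.1 is to the same effect.

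**What is recorded.** Item 2 of the Appendix B questionnaire asks "What was the name of the drug you reacted to", and the subject may answer that it is unknown. Low-risk status (6.1.2.1) depends on symptoms and timing, not on the drug.

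**The concern.** For someone who reacted only to a cephalosporin, the reference standard tests a different drug from the one reported. By the protocol's own account of cross-reactivity, a negative penicillin skin test and a tolerated amoxicillin dose say little about that person's reported allergy. The plan still scores the person as negative for PCN (B-lactam) allergy and pools the result in the prevalence, the NPV, the item NPVs and the derivation of the short questionnaire.

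Two things are at stake. First, the primary conclusion would claim absence of B-lactam allergy in people for whom that was not verified; section 2.1 names ceftriaxone as first-line gonorrhoea therapy, so the distinction matters in these clinics. Second, the symptom answers of these subjects are paired with an outcome for another drug when items are chosen for the short questionnaire.

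**Working it through.** **1. The plan's own figure.** Inputs from protocol 8.2: sensitivity 0.85, specificity 0.95, prevalence and observed share 3%, target bound 98.4%, power 85%, 5% level, 5% not tested.

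- NPV = 0.95 × 0.97 / (0.95 × 0.97 + 0.15 × 0.03) = 99.51%, as stated.
- Negative likelihood ratio expected: 0.15/0.95 = 0.1579. At the bound: (0.016/0.984) × (0.97/0.03) = 0.5257. Log ratio 1.2029.
- Variance term: 0.85/(0.15 × 0.03) + 0.05/(0.95 × 0.97) = 188.94.
- n = 188.94 × (1.645 + 1.036)² / 1.2029² = 938.8; divided by 0.95 this is 988.2, matching 988. This match needs a one-sided 5% level.

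**2. Shift in the penicillin NPV from pooling.** Let c be the cephalosporin-only share among those tested, p the reference-positive rate in penicillin reporters and q the rate in cephalosporin-only reporters. The pooled NPV exceeds the penicillin-only NPV by c × (p − q). The documents give neither c nor q. I assume c = 5%, 10% or 20%. As a stand-in for q, I take the ratio from the STD-clinic study in section 2.1: 1.7% skin reactivity without an allergy history against 7.1% with one, so q = p × 1.7/7.1 = 0.239p and the shift is 0.761 × c × p.

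| p | c = 5% | c = 10% | c = 20% |
|---|---|---|---|
| 3% (planning prevalence) | 0.11 points | 0.23 | 0.46 |
| 0.49% (100% − 99.51%) | 0.02 | 0.04 | 0.07 |

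At p = 3% the pooled prevalence of reactivity would read 2.89%, 2.77% or 2.54%.

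**3. The direction is not fixed.** If q is instead the absolute 1.7% and p is 0.49%, the shift at c = 20% is 0.20 × (0.49 − 1.7) = −0.24 points, so pooling would lower the NPV. With q = 0 the shift at c = 20% is +0.10 points.

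**4. The B-lactam reading.** Suppose 945 of 950 tested are negative: 99.47%, two-sided exact lower bound 98.78%. Suppose further that 3% of 95 or 190 cephalosporin-only subjects (about 3 or 6 people) have an allergy that the penicillin tests miss. The 3% is an assumption without support in the documents.

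| Truly negative | NPV | Two-sided 95% lower bound | One-sided 95% lower bound |
|---|---|---|---|
| 942/950 | 99.16% | 98.35% | 98.49% |
| 939/950 | 98.84% | 97.94% | 98.09% |

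All four bounds clear the 97% that section 8.2 gives for a useless test. Against 98.4%, the first row falls short by 0.05 points on the SAP's two-sided scale and passes on the one-sided scale that reproduces 988.

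**5. Cost of restricting the primary set.** Of 988 enrolled, 988 × 0.95 × (1 − c) penicillin reporters would be tested: 892, 845 or 751. Power = Φ(√(n/188.94) × 1.2029 − 1.645) = 83.4%, 81.6% or 77.4%, against 85% planned.

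**The case against.** A reader might infer that cephalosporin-only reporters are near-automatic negatives who materially inflate the primary NPV, so that they must be removed from the primary analysis. The documents do not support that.

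- The share of such people is not given, and the 1.7/7.1 ratio comes from skin tests in people with no allergy history, not in cephalosporin reactors.
- Low-risk penicillin reporters are themselves almost all negative: sections 2.2.3 and 2.2.4's neighbouring background cite 1.5% cutaneous reactions on direct challenge in military recruits, and 0.2% acute plus 1.1% delayed in a large health-plan programme. The contrast between the groups may be slight.
- Section 2.2.5 excepts a few early-generation cephalosporins from its reassurance, so some cephalosporin reporters may react.
- For penicillin allergy, a cephalosporin-only subject who tests negative is a correct negative; only the case mix changes.

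Examples can be built in which pooling moves a bound across 97%. With 939 tested, a 20% share and 15 positives, all penicillin reporters, the two-sided lower bound is 97.38% pooled (924/939) and 96.73% in penicillin reporters alone (736/751). That is a chosen configuration, not a forecast.

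Two further defences carry some weight. Broad eligibility looks deliberate, since most passages say PCN or B-lactam. And item 2 is not wholly outside the analysis: protocol 8.4.1 plans an NPV for each question, the questionnaire items are candidates for the short form, and SAP 7.2 summarises allergy history. But SAP 7.3 limits item NPVs to the low-risk items, and neither document has a coding rule, subgroup or sensitivity analysis by index drug. None of these points answers the mismatch between a B-lactam target and a penicillin-only reference standard.

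**Conclusion.** The point stands as a mismatch between the target and the reference test. Eligibility admits non-penicillin B-lactam reporters, all testing is with penicillins, the protocol says cross-reactivity is limited, and the SAP still reports an NPV for PCN (B-lactam) allergy with everyone pooled. That holds whatever the numbers are, and it limits what the trial can conclude.

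The numerical effect on the penicillin NPV is uncertain in size and direction. Under assumed shares of 5% to 20% and the 1.7/7.1 ratio, it is 0.11 to 0.46 points at 3% prevalence and 0.02 to 0.07 points at the planned 99.51%. It should not be presented as a demonstrated inflation of the primary result.

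**What to change.** 1. In protocol 3.2.1, 8.1.1 and 8.4.1 and SAP 3.1 and 7.3, state the primary target as penicillin allergy.
2. Write a coding rule for questionnaire item 2. Keep the full Treated population as planned and add a pre-specified sensitivity analysis of prevalence, NPV, item NPVs and short-questionnaire derivation in subjects whose index drug is a penicillin or unknown. Add a run excluding unknown index drugs, because some of those may be cephalosporins. Describe cephalosporin-only and other non-penicillin B-lactam reporters separately.
3. Reconcile the counselling wording in protocol 6.3.1 and 6.3.3 with section 2.2.5 and with what was tested.

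The cost is a narrower claim, some extra programming on a field already collected, and lower precision in the restricted analysis. Making the restricted set the primary one is a trade-off rather than a requirement, given the power loss shown in step 5 of the working.

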5.2.2 Subject Exclusion Criteria

Subjects meeting any of the following criteria at baseline will be excluded from study participation:

- Not able to stay for testing and challenge (1-3 hours) on day of clinic visit (or return within 6 weeks to complete study procedures)
- Other exclusion criteria, per clinical judgment, which prohibits enrolling in study

5.3 Pregnant Subjects

There is no contraindication to enrolling pregnant subjects and administering the questionnaire or performing skin testing. PCN skin testing is safe in this population and is frequently performed. Pregnant women will not undergo the direct oral challenge with amoxicillin to verify PCN allergy. Pregnant women will be enrolled in the PST Group, complete the questionnaire, and have skin testing performed. If necessary, pregnant women may return to the clinic within 6-weeks to complete the skin testing. Pregnancy will be determined by self-report and/or the

standard procedures employed in the participating clinic to diagnose pregnancy when clinically indicated. All clinics have access to point-of-care pregnancy tests.

There is substantial benefit in pregnancy of “delabeling” a PCN (B-lactam) allergy since PCN is the only recommended therapy for syphilis in pregnancy, and B-lactam drugs are the preferred treatment for bacterial infections, such as amoxicillin for Group B streptococcus (GBS) and ceftriaxone for gonorrhea. The ambulatory STD settings in this study service patient populations at higher risk of GBS.

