4.1 Assignment to Intervention Group (PST or DOC)

Each site will perform both allergy validation interventions, Method 1 PST Group and Method 2 DOC Group. The anticipated enrollment at each site will be 200 subjects overall; 100 in each group. Since each intervention has different logistical considerations, sites will enroll subjects in sequential block groups of 25. Sites will be assigned the order of block groups randomly.

For example, sites that are assigned to begin with PST will enroll the first 25 subjects into the PST group, then follow with 25 subjects in the DOC group, then PST, etc. until the full 200 are enrolled. Similarly, sites assigned to start with the DOC intervention will enroll the first 25 subjects using the DOC, followed by 25 in PST, then DOC etc., until the full 200 are enrolled. Therefore, each site will enroll 8 block groups, 4 in each allergy validation intervention.

Method 1: Enrollment in the PST Group

Site staff will review the responses from the allergy history screening questionnaire to identify subjects who have low-risk criteria for immediate hypersensitivity (see Sec 6.1.2.1). These subjects will receive penicillin skin testing. All subjects who have negative skin tests will be offered a one-step oral challenge for final validation. Subjects who report higher-risk criteria will be referred to an allergy provider.

Method 2: Enrollment in the DOC Group

Site staff will review the responses provided on the allergy history screening questionnaire to identify subjects who have low-risk criteria for immediate hypersensitivity (see Sec 6.1.2.1).

These subjects will be offered a two-step direct oral amoxicillin challenge to validate absence of allergy. Subjects who report higher-risk criteria will be referred to an allergy provider.

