7.1.3 Oral Challenge

Pregnancy status will be verified. Pregnant women will not be enrolled in the DOC group.

Prior to the oral challenge, vital signs will be recorded (heart rate, respiratory rate, blood pressure and peak flow). A focused PE will be performed (eyes, pharynx, lungs and skin). Subjects will be observed for 60 minutes \pm 10 minutes after the amoxicillin is administered. Vital signs, peak flow measurement and focused PE will be repeated after the 60-minute observation period \pm 10 minutes.

After oral challenge, subjects will be assessed for the most common elicited reactions associated with amoxicillin which will be graded and documented using the Toxicity Table (Appendix C):

- Cardiovascular: lightheadedness, loss of consciousness
- Skin: urticaria, flushing, rash, angioedema
- HEENT: conjunctivitis, rhinitis, congestion
- Respiratory: shortness of breath, wheezing
- GI: nausea, vomiting, diarrhea

Data will be collected on reactions to amoxicillin as a diagnostic tool for defining an allergic reaction that was not identified by the skin testing. Unanticipated reactions that place the subject at increased risk will be recorded on the AE CRF and reported to the IRB and DMID according to their reporting guidelines.

Subjects will be provided with contact information for study staff to report the development of additional symptoms.

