7.4 Analysis of Secondary Objective

For the following measures, the frequencies and the percentages with corresponding exact 95% confidence intervals of participants will be tabulated by intervention group (if available), , study site and overall in the following measures.

7.4.1 Assessment of Subject Acceptability/Feasibility:

In the Eligible Population:

- those who refuse to participate in the study. The reasons of not interested in participating in the study will be summarized.

- For those who prefer to see an allergist for skin testing, summarize the reasons why they have not seen an allergist until now.

In the Treated Population:

- those who experience elicited reactivity to PCN allergy skin testing in the PST Group and oral challenge by dosage and group.
- those who find the testing procedures of to be helpful. The reasons of finding the PCN testing not helpful will be summarized.
- Those feeling comfortable with allergy testing conducted in settings where STD services are provided rather than by an allergist.
- chance of referring a friend or family member having a history of penicillin allergy.
- confidence in taking PCN or similar antibiotics among those who have been skin tested and are negative for PCN allergy.

7.4.2 Assessment of Provider Acceptability/Feasibility:

In the Provider Population, summarize by group (if possible) in numbers and proportion of:

- those who prefer PCN skin testing, direct oral challenge, or no preference.
- those who feel PCN allergy assessment can be performed safely and effectively in a setting which treats patients with STIs.
- those who will offer PCN allergy assessment in the future.
- reasons why study providers will not offer PCN allergy assessment in the future.

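### All pregnant participants go to PST and none to DOC, so the secondary by-group tables differ in pregnancy mix by rule, and SAP 7.2 would not show it

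*Protocol*

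**What the plan says.** **Assignment.** Protocol 4.1 has sites work through blocks: "sites will enroll subjects in sequential block groups of 25". What is randomised is the sequence: "Sites will be assigned the order of block groups randomly". The target is stated as "The anticipated enrollment at each site will be 200 subjects overall; 100 in each group". The section gives no exception for pregnancy and no rule for counting pregnant women toward a block.

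**Pregnancy.** It is not an exclusion criterion (Protocol 5.2.2), and Protocol 5.3 argues for including these women. That section states "Pregnant women will be enrolled in the PST Group, complete the questionnaire, and have skin testing performed" and "Pregnant women will not undergo the direct oral challenge with amoxicillin to verify PCN allergy". Protocol 7.1.3 repeats the bar: "Pregnant women will not be enrolled in the DOC group".

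**Reporting.** Protocol 8.4.2 evaluates the secondary endpoints by intervention group as well as overall. SAP 7.1 (disposition), 7.2 (baseline), 7.4 (acceptability and reactivity), 7.5 (oral challenge results) and 7.7 (adverse events) all call for by-group summaries. None is restricted, stratified or adjusted for pregnancy. SAP 7.2 places current pregnancy status among the items summarised only for DOC.

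**The concern.** By rule, one group contains every pregnant participant and the other contains none. A reader who sets the PST column beside the DOC column will take differences in age and sex mix, reactivity or acceptability as differences between methods. Part of any such difference may come from who was allowed into each group, and enrolling more people does not remove it.

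The baseline table makes this harder to notice. Pregnancy status is planned for the group where the answer is fixed in advance and omitted for the group where it varies.

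What is at stake is the interpretation of the secondary by-group results on acceptability, feasibility and elicited reactions. The primary results are not at stake.

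**Working it through.** **1. The plan's own figure.** The documents give no sample size or power for PST v DOC. The only figure is 988, for the pooled NPV. Inputs (Protocol 8.2): sensitivity 0.85, specificity 0.95, prevalence 0.03, lower bound 0.984, power 85%, level 5%, and 5% lost to high-risk history.

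- NPV = 0.95 × 0.97 / (0.95 × 0.97 + 0.15 × 0.03) = 0.9215 / 0.9260 = 0.9951.
- N = (z_alpha + z_power)² × [sens/(1 − sens)/prev + (1 − spec)/spec/(1 − prev)] / [logit(NPV) − logit(0.984)]².
- With a one-sided 5% level, N = 938.8, and 938.8 / 0.95 = 988.2, against 988 stated.

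No term refers to the group or to pregnancy, so the imbalance does not alter this figure.

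**2. Concentration in PST.** SAP section 1 gives five sites, and 5 × 100 = 500 per group. The documents give no pregnancy share, so 1%, 2%, 5% and 10% of 1,000 enrolled are assumed, with group totals held at 500. All of these women are in PST:

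| Pregnant, all enrolled | Women | Share of PST | Share of DOC |
|---|---|---|---|
| 1% | 10 | 2% | 0% |
| 2% | 20 | 4% | 0% |
| 5% | 50 | 10% | 0% |
| 10% | 100 | 20% | 0% |

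**3. Shift in the reactivity difference.** Take 3% reactivity in non-pregnant participants (the prevalence in the Protocol 8.2 example) and assume r = 0% to 9% in pregnant women. With s the pregnant share of PST, the shift is s × (r − 3%).

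- 1% pregnant (s = 0.02): -0.06 to +0.12 points.
- 2% (s = 0.04): -0.12 to +0.24 points.
- 5% (s = 0.10): -0.3 to +0.6 points.
- 10% (s = 0.20): -0.6 to +1.2 points.

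The standard error of the difference at 500 v 500 is √(2 × 0.03 × 0.97 / 500) = 1.08 points. The Protocol Summary gives four sites. With 400 v 400 the shifts are the same and the standard error is 1.21.

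**4. Share challenged.** Protocol 4.1 offers the one-step challenge to every PST subject with a negative skin test, and 6.2.1 uses it to confirm absence of allergy. Protocol 5.3 lists only the questionnaire and skin testing for pregnant women, and mentions only skin testing for their return visit. What it rules out is the direct challenge, which is the name of Method 2. There are two readings:

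- Pregnant women take the one-step challenge: this rule does not change the share challenged.
- They have skin testing only: the PST share challenged falls by at most s, that is up to 10 points at 5% pregnant overall.

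The documents do not settle which reading applies.

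**5. Precision after restriction.** The half-width is 1.96 × √[0.03 × 0.97 × (1/n₁ + 1/500)], with n₁ the non-pregnant PST participants.

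| n₁ | 500 | 490 | 480 | 450 | 400 |
|---|---|---|---|---|---|
| Half-width (points) | 2.11 | 2.13 | 2.14 | 2.17 | 2.24 |

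**The case against.** The strongest reply is that nothing formal depends on PST v DOC. The primary prevalence and NPV pool both methods, and the by-group output consists of frequencies, percentages and single-group intervals. SAP section 5 mentions comparisons between treatment groups only when it declines a multiplicity adjustment; no such test is specified. This stands, and it limits the point to descriptive secondary tables.

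The groups were also never individually randomised. Blocks alternate in known order, and the pre-skin-test checks in Protocol 7.1.1 (antihistamines, skin disease, large tattoos) may separate the groups further. This stands too: pregnancy is one departure among several, and removing it does not make the groups exchangeable.

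A reader might infer more than the text supports in three ways:

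- *That pregnant women are inserted into PST while a DOC block is open.* Protocol 5.3 and 7.1.3 do not mention blocks. Deferral to the next PST block is equally compatible with them. The mix differs by rule either way.
- *That pregnant women have no oral challenge, so PST's challenge rate falls.* This is one of two readings; on the other the fall is zero. In addition, SAP 7.5 summarises results after each dose, so unchallenged women would not dilute that table. The share challenged differs by design anyway, because skin-test positives stop before challenge.
- *That the primary results or the 988 are compromised.* They are pooled, and the imbalance does not enter them.

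The objection does not answer the reporting gap. By-group results are planned, readers will compare the columns, and the baseline table omits the characteristic on which the groups are known to differ.

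**Conclusion.** The point holds as a limited defect in the secondary reporting. PST and DOC differ in pregnancy mix by rule, Protocol 4.1 does not acknowledge this, and SAP 7.2 as written would leave it out of view.

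The size cannot be determined from the documents. At an assumed 5% pregnant among all enrolled, with reactivity of 3% in others and 0% to 9% in pregnant women, the reactivity difference moves by about -0.3 to +0.6 points, which is small beside a standard error of 1.08. At 10% pregnant the range is -0.6 to +1.2 and no longer clearly small. An effect on acceptability is possible, but there are no figures from which to size it. An effect on the share challenged is conditional on how Protocol 4.1, 5.3 and 6.2.1 are reconciled.

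The documents do not support calling this a breakdown of the allocation or a threat to the primary analysis. The correction is still worth making: it removes a known difference from the planned tables at little cost.

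**What to change.** 1. **SAP 7.2:** record and tabulate pregnancy status for PST as well as DOC.
2. **SAP 7.1, 7.2, 7.4, 7.5 and 7.7:** show PST and DOC side by side in non-pregnant participants. Report pregnant participants separately in summary form, since a full column in every table could give very small cells. Keep them in the overall totals. Add a note that criteria specific to skin testing may still make the groups differ.
3. **Protocol 4.1:** state the pregnancy exception and how these women count toward the blocks of 25.
4. **Protocol 4.1, 5.3 and 6.2.1:** reconcile the text on whether the one-step challenge applies to pregnant women. Which way is a clinical decision and is not proposed here.

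**Cost.** The PST column in the side-by-side tables becomes slightly smaller: at an assumed 5% pregnant, 450 v 500, with the half-width going from 2.11 to 2.17 points. One pregnancy field has to be captured for PST. Protocol 5.3 already has pregnancy determined by self-report or clinic procedures, but the SAP does not show that the result is available for PST. No extra enrolment and no separate enrolment stratum are needed.
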